Patients potentially eligible for this study are at least 18 years of age and have histologically confirmed necrobiosis lipoidica diabetorum. A total of 18 subjects will be enrolled in the study. Potential patients will be assessed for eligibility to participate in this clinical study using the criteria for inclusion and exclusion listed under “Subject Selection” section.

Methods

Study Endpoints:

1. Primary Endpoint

- **Proportion of patients achieving remission or clinical improvement based on Investigator Global Assessment Score as measured at week 24.**

2. Secondary Endpoints

- **Proportion of subjects achieving improvement based upon histological score**
- **Proportion of subjects improving based upon patient-reported outcomes (pain score and Dermatology Quality of Life Index Score)**

Investigator Global Assessment (IGA) of Efficacy Score (See Investigator Global Assessment of Efficacy Score)

(adapted from scoring system for published pyoderma gangrenosum trials)

Score	Description
0	Completely clear: except for possible residual hyperpigmentation
1	Almost clear: very significant clearance (about 90%); however, patchy remnants of dusky erythema and/or very small ulcerations
2	Marked improvement: significant improvement (about 75%); however, a small amount of disease remaining (i.e. remaining ulcers, although have decreased in size, minimal erythema and/or active boarder)
3	Moderate improvement: intermediate between slight and marked; representing about 50% improvement
4	Slight improvement: some improvement (about 25%); however, significant disease remaining (i.e. remaining ulcers with only minor decrease in size, erythema or boarder activity)
5	No change from baseline
6	Worse

Scoring system based on the following trial [4]:

An open-label pilot study of alefacept for the treatment of pyoderma gangrenosum. European Academy of Dermatology and Venereology 2008 22, pp943–949

Histological Score

- a. Inflammatory infiltrate (0, none; 1, slight; 2, moderate; 3, severe)
- b. collagen degeneration (0, none; 1, slight; 2, moderate; 3, severe)
- c. epithelioid histiocytes, (0, none; 1, slight; 2, moderate; 3, severe)
- d. qualitative expression of IL-17 (0, none; 1, slight; 2 moderate; 3, severe)

Scoring system based on the following trial [5]:

Fumaric acid esters in necrobiosis lipoidica: results of a prospective noncontrolled study. British

Journal of Dermatology 2005 153, pp802–807

Patient-Reported Outcomes

Pain Score

- _(i) Resolved

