Laboratory reference ranges will be obtained prior to the initiation of the study. The Baseline laboratory test results for clinical assessment for a particular test will be defined as the last measurement prior to the initial dose of study drug.

Whether action needs to be taken to address notable laboratory values will be decided by the investigator, taking into account the overall status of the subject.

The following laboratory tests will be performed according to the study procedures schedule listed in Overview of Study Procedures:

- Complete Blood Count (CBC): automated WBC, RBC, hemoglobin, hematocrit, platelet count

and RBC indices

- Complete Metabolic Panel (CMP): Sodium, Potassium, Chloride, Bicarbonate, BUN, Creatinine, Glucose, Alk Phos, ALT, AST, Total Bilirubin, GGT, Albumin, Albumin/Globulin Ratio (calculated), BUN/Creatinine Ratio (calculated), Calcium, Globulin (calculated), Total Protein
- HIV: HIV1&2 Antibody/Antigen Combo Assay
- Hepatitis B: Hep B Core Ab (Hep B Cab), Hep B Surface Antigen (Hep B Sag), and Hep B surface antibody (Hep B Sab)
- Hepatitis C: Hepatitis C antibody
- Tuberculosis: Quantiferon-TB Gold

Subjects who test positive for TB (quantiferon gold), Hepatitis C antibody, or Hepatitis B Sag or Hepatitis B Core antibody will be excluded from the study. Patients with a positive quantiferon gold will be referred to ID. If a patient has an indeterminate quantiferon gold that test will be repeated. If there are two indeterminate quantiferon gold results, then the patient will be referred to ID. If ID thinks the patient (with an indeterminate quant gold) needs to be treated for latent TB, then the patient will be treated for latent TB (see below). If ID does not think the patient (with an indeterminate quant gold) needs treatment for latent TB then the patient will be eligible to enroll in the clinical trial

After one month of treatment for latent TB, a subject would be considered eligible for participation in the trial.

Skin Biopsy

A 4 mm punch biopsy will be obtained from lesional skin at the baseline and week 26 visit. Skin biopsy location will be determined by the investigator and standard procedures for skin biopsy will be employed. Subjects may have lesions closed with suture or gelfoam, depending on nature of lesion and biopsy.

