The clinical efficacy will be measured by physician assessments and standardized scoring tools as noted in Main Study Parameters and Secondary Parameters. Because of the small number of patients in the study, and absence of a control group, primarily descriptive statistics will be used to report data from measured endpoints.

Main Study parameters

Primary Endpoint

- Proportion of patients achieving remission or clinical improvement based on Investigator Global Assessment Score as measured at week 24.

We will assess the proportion of patients achieving remission or clinical improvement based upon the previously published Investigator Global Assessment Score. Remission correlates with a score of 0 or 1 and clinical improvement correlates with at least a -1 change from baseline.

Secondary study parameters

Secondary Endpoints

Because of the small sample size, primarily descriptive statistics will be used.

- Proportion of subjects achieving improvement based upon histological score
- Proportion of subjects achieving improvement based upon patient-reported outcomes (pain score and Dermatology Quality of Life Index Score)

Other study parameter(s)

Patient characteristics and demographic data will be presented using descriptive statistics.

Histological Score

In addition, a histological score will be calculated as a secondary endpoint. The score is calculated by adding sub scores as listed below, which will be evaluated by the dermatopathologist. Average of pre and post scores and overall change in score will be calculated and compared using a paired T-test. See Secondary Study Parameters for details regarding histologic analysis.

Pain Score

A Pain Score will be calculated based upon the Wong-Baker 10-point pain score, which has been widely used to rate pain in both children and adults and has also been used in dermatology clinical trials.[6]

Response based on an improvement from baseline in the Wong-Baker pain score at all scheduled time points will be calculated. We will compare pre and post treatment pain values and categorize patients as

Dermatology Life Quality Index (DLQI)

A Quality of Life Score will be calculated based upon the Dermatology Life Quality Index (DLQI).

C. Subject Selection

Inclusion Criteria

A subject must meet all of the following criteria in order to be eligible to participate in this study:

1. Adults, age 18 and over
2. Previous diagnosis of biopsy-proven NLD
3. Active NLD lesions, defined as

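### The end-of-treatment biopsy must come from lesional skin, so histology may be missing or unrepresentative in subjects who clear or nearly clear

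*Combined protocol and SAP*

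**What the plan says.** Section B3.A, Skin Biopsy, covers both time points in one sentence: "A 4 mm punch biopsy will be obtained from lesional skin at the baseline and week 26 visit". The next sentence leaves the site open: "Skin biopsy location will be determined by the investigator and standard procedures for skin biopsy will be employed". *Lesional* is not defined. Nothing ties the second punch to the lesion sampled at baseline, and nothing covers the case where no lesion remains. The Early Termination Visit repeats the Week 26 procedures, so the same gap applies there.

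The IGA table in B3.A makes full clearance a possible outcome. Score 0 is "Completely clear: except for possible residual hyperpigmentation" and score 1 is "Almost clear: very significant clearance (about 90%); however, patchy remnants of dusky erythema and/or very small ulcerations". Section B3.B builds the primary endpoint on these scores: "Remission correlates with a score of 0 or 1 and clinical improvement correlates with at least a -1 change from baseline".

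Histology is a secondary endpoint in B3.B: "Proportion of subjects achieving improvement based upon histological score". The analysis under Histological Score is paired: "Average of pre and post scores and overall change in score will be calculated and compared using a paired T-test". No denominator is given for the proportion, and there is no rule for a missing second biopsy. The section on evaluation of immunohistochemistry also compares IL-17A expression before and after treatment, using the same two biopsies.

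**The concern.** The site rule refers to the state of the skin at the time of sampling, and treatment is meant to change that state. Followed to the letter, the rule makes the second histological measurement conditional on residual disease. A subject at IGA 0 could have no compliant sample. A subject at IGA 1 could be sampled only in the roughly 10% of disease that remains.

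Whether a histological result exists, and what tissue it describes, could then depend on the primary outcome. The proportion improving and the mean change would lean towards subjects who did not clear, and histology could appear to contradict a good clinical result. The IL-17A comparison, which tests the mechanism behind the trial's rationale, would have the same weakness.

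**Working it through.** The plan gives no sample size calculation and no expected response rate, so there is no figure to reproduce. The check has two parts.

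**1. The texts side by side**

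| End-of-treatment state | Compliant site if lesional means clinically diseased | Compliant site if lesional includes the former lesion |
|---|---|---|
| IGA 0 | none | treated area |
| IGA 1 | remnants only | treated area or remnants |
| IGA 2 or above | remaining disease | treated area or remaining disease |

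Both readings are open. They give different tissue from the same subject and, at IGA 0, a different set of analysed subjects. A paired t-test cannot use a subject who has only one score. Strictly, only IGA 0 can lack lesional skin. At IGA 1 the issue is which tissue is sampled.

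**2. Possible size if cleared subjects have no second biopsy**

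Input from the plan: N = 18 ("A total of 18 subjects will be enrolled in the study"). Assumptions, none of them in the documents: c subjects clear, all c would show histological improvement if sampled at the former lesion, and a proportion p of the other subjects improves, with p between 30% and 50%.

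- All sampled: (c + (N − c)p)/N = p + (c/N)(1 − p)
- Cleared subjects missing: p
- Understatement: (c/N)(1 − p)

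| c | p | All sampled | Cleared missing | Understatement |
|---|---|---|---|---|
| 0 | any | p | p | 0 |
| 1 | 30% | (1 + 17 × 0.3)/18 = 33.9% | 30% | 3.9 points |
| 1 | 50% | (1 + 17 × 0.5)/18 = 52.8% | 50% | 2.8 points |
| 4 | 30% | (4 + 14 × 0.3)/18 = 45.6% | 30% | 15.6 points |
| 4 | 50% | (4 + 14 × 0.5)/18 = 61.1% | 50% | 11.1 points |

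The assumption of 100% improvement in cleared subjects drives the size. If they improved histologically only as often as the others, the understatement would be zero.

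The mean change behaves in the same way. The four sub-scores of 0 to 3 sum to 0 to 12. Assume a change of −6 in cleared subjects and −1.5 in the rest. The mean over all 18 is (1 × −6 + 17 × −1.5)/18 = −1.75 with one cleared, and (4 × −6 + 14 × −1.5)/18 = −2.50 with four. Without the cleared subjects it is −1.50 in both cases.

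The passage on the follow-up call after study completion mentions 3 completers and 1 early termination. If the analysis had only 4 subjects, one missing cleared subject would matter more: 3/4 against 2/3 is 8 points, and 2/4 against 1/3 is 17 points.

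**The case against.** The strongest reply is that the documents nowhere exempt a cleared subject from biopsy. The investigator chooses the location, the evaluation schedule lists the end-of-treatment biopsy without a clinical condition, and every histological item has a zero category, so disease-free tissue can be scored. A punch into a hyperpigmented former lesion may be exactly what was intended. This stands, and it is why the loss is stated only as a possibility. It does not close the gap: discretion over location sits beside the requirement for lesional skin and does not clearly override it.

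A reader might infer that the rule removes the best responders and so biases histology against the drug. The documents do not support that. Remission includes IGA 1, where diseased skin remains. The text permits sampling of remnants but does not plainly compel it. With the investigator free to choose, sampling could also favour the drug, so the direction is not fixed.

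It is also fair that clearance may be rare. IGA 0 tolerates only residual hyperpigmentation, while the Background describes plaques that become atrophic and yellow. Finally, the endpoint is secondary, in an uncontrolled pilot reported mainly with descriptive statistics. That limits the weight of the point, but the correction is cheap.

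**Conclusion.** The point holds in a limited form. The plan applies a single lesional-skin rule to both biopsies, defines an outcome in which such skin may no longer exist, and then analyses paired scores with no rule for a missing one. Histology and the IL-17A comparison may therefore be missing or unrepresentative in subjects who clear or nearly clear.

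With nobody cleared, no subject is lost and the understatement is nil. Under the stated assumptions it is about 3 to 4 points for 1 cleared subject in 18 and 11 to 16 points for 4 in 18. The number clearing and both histological improvement rates are assumptions. The effect of sampling remnants at IGA 1 cannot be quantified from the documents. The primary endpoint is not affected. The change is worth making because it costs little and protects the trial's only tissue-based results.

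**What to change.** **Skin Biopsy (B3.A).** For the second biopsy, replace the lesional-skin requirement with a site fixed in advance. It should lie in the same lesion as the baseline biopsy, next to but outside the baseline biopsy scar. It should be chosen and documented at baseline, for example on the baseline photograph, and used whether or not the skin has cleared. Specifying only the baseline lesion area would not be enough, because the investigator could still choose between cleared and residual spots. The sentence on investigator choice of location should be revised in the same edit, since both problems come from the missing link between the two sites.

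**Secondary Endpoints and Histological Score (B3.B).** Report the number of subjects with paired biopsies, and the number without a second biopsy together with their IGA. Give the proportion improving out of all subjects with a baseline biopsy. If any second biopsies are missing, add a range that counts those subjects first as not improved and then as improved. For example, with 18 baseline biopsies, 2 missing second biopsies and 6 of the other 16 improved, the range is 6/18 (33%) to 8/18 (44%).

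**Timing.** The text puts the second biopsy at week 26, while the evaluation schedule, as extracted, appears to place it at week 24 with suture removal at week 26. The two should be reconciled.

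**Cost.** A few sentences and no additional biopsy. Some of the punches already planned would fall in clinically cleared skin, with the biopsy risks listed in B5 (bleeding, pain, infection, scar). A range replaces a single figure if samples are missing. For subjects who have already finished, only the reporting part can be applied.

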PROTOCOL DOCUMENT WITH STATISTICAL ANALYSIS INCLUDED

Title: Secukinumab for NLD (Cosentyx) in Patients With Necrobiosis Lipoidica Diabeticorum (NLD)

NCT: NCT03791060

Document Date: 11-10-2020

PART B STUDY DESCRIPTION

TITLE OF PROTOCOL	An open-label proof of concept study regarding the use of Secukinumab (Cosentyx) in patients with necrobiosis lipoidica diabetorum (NLD)
Principal Investigator	[name]

B1. PURPOSE OF PROTOCOL

The objective of this study is to evaluate whether the IL-17 inhibitor, secukinumab shows evidence of efficacy in the treatment of Necrobiosis Lipoidica Diabetorum (NLD).

B2. SIGNIFICANCE AND BACKGROUND FOR THE STUDY

Background:

Necrobiosis lipoidica diabetorum (NLD) is a rare granulomatous condition of the skin that is over-represented in patients with diabetes. Classically, this condition presents with papules and plaques, most commonly on the distal extensor lower extremities. These plaques can become atrophic over time displaying a characteristic yellow hue, and may subsequently ulcerate. Although in many patients the lesions are not painful, in approximately 25% of patients the lesions can be very painful, particularly among patients who develop ulcerations.

The nature of the relationship between NLD and diabetes mellitus is poorly understood. The incidence of NLD in people with diabetes mellitus is estimated to be 0.3% to 1.2%. Initial studies from the 1960's suggested that approximately 60% of patients with NLD also had diabetes, however subsequent studies reported lower estimates of diabetes in patients with NLD (11%), and further epidemiologic studies have not been performed.

The condition may be challenging to manage, as currently no FDA-approved treatment exists, and no well-established treatment algorithm has been described. Reports on successful therapeutic interventions have generally been small and inconsistent.

The pathogenesis of NLD is poorly understood, however associations with vascular changes and immune dysregulation have been explored. Recent literature has suggested a potential role for IL-17 in the development of this condition. In 2012, Wakusawa et al reported a case of a 37 year old woman with NLD and insulin dependent diabetes mellitus. Immunohistochemical staining was performed on a biopsy specimen and revealed a significant number of IL-17 positive cells present throughout the granuloma. [1]

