- (ii) Improved
- (iii) Stable
- (iv) Worsened

Dermatology Life Quality Index (DLQI)

A Quality of Life Score will be calculated based upon the Dermatology Life Quality Index (DLQI). The DLQI is a validated general dermatology questionnaire that consists of 10 items that assess subject health-related quality of life (daily activities, personal relationships, symptoms and feelings, leisure, work and school, and treatment) (See Dermatology Life Quality Index). [7] It has been extensively used in dermatology clinical trials for AD. The DLQI is a psychometrically valid and reliable instrument that has been translated into several languages, and the DLQI total scores have been shown to be responsive to change. The minimally important difference for the DLQI has been estimated as a 2 to 5 point change from baseline.

Other study parameters

Safety Parameters

Safety evaluations include adverse event (AE) monitoring, physical examinations, vital sign measurements, and clinical laboratory testing (hematology and chemistry) as a measure of safety and tolerability for the entire study duration.

At every visit adverse events will be registered.

Randomization, blinding and treatment allocation

This is an open-label proof of concept study. There will be no randomization or blinding. All subjects will receive study treatment.

Study Procedures

Prior to performing any study related procedures, the investigator will discuss with each subject the nature of the study, its requirements and its restrictions. A written informed consent form will be obtained from each participant prior to any procedure.

Each subject with a signed informed consent form will be screened at the first visit, to ensure all the inclusion criteria are met and none of the exclusion criteria.

Study procedures are described in detail below and an overview of the study procedures during each visit.

Medical history

- A complete medical history, including history of diabetes, will be taken at screening. The subject's medical history will be updated at the Baseline visit. This updated medical history will serve as the baseline for clinical assessment.
- Demographic information, including subject self-reported gender, race, age, ethnicity, and child-bearing potential will be recorded.
- Nicotine and alcohol history will be obtained

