Skin biopsies will be sent to Dermatopathology lab at BIDMC for further Immunohistochemistry analysis as below. Samples will be preserved in formalin jars and sent to the histology lab to be processed within 48 hours. The paraffin blocks will be sectioned and stained at the histology lab, and then blocks and slides will be returned to the Dermatopathologist and stored securely at BIDMC, Dept of Pathology. Samples are retained for the duration of the project, through publication. If all

members of the study team deem they are no longer needed, they will then be destroyed.

Immunohistochemistry

Each biopsy will be fixed in formalin, bisected vertically, dehydrated by routine histologic methods, and embedded in a paraffin block. 5- μ m-thick surface sections will be cut, mounted on glass slides, and baked for 60 minutes at 60C. The first slide will be stained with Hematoxylin and Eosin. The next slide will be loaded into the Bond III staining platform and antigen retrieved by immersion in Bond Epitope Retrieval 2 for 30 minutes. It will then incubated at room temperature for 30 minutes with Anti-Human IL17A antibody [Abcam 4K5F6] at a concentration of 0.5–10 μ g/ml. After appropriate washes, antibody detection will be performed using Bond Polymer Refine Detection kit. Slides will be developed in DAB, then dehydrated and coverslipped. A biopsy of an active psoriatic skin lesion and a slide of the case with no antibody applied will be run in parallel as positive and negative controls, respectively.

Evaluation of immunohistochemistry

IL-17A expression levels will be scored as follows: A three tier stratification threshold for percentage of positive lymphocytes will be established after review of the pre-treatment biopsies, and classified as absent, low, or high. Cellular staining intensity will be scored as 0 (no staining), 1 (weak staining), 2 (moderate staining), or 3 (strong staining).

Pre- and post-treatment expression levels will be compared using Fisher's exact test. Pre-treatment IL17A expression level will be compared with clinical response parameters and evaluated as a possible predictor of response to therapy.

In case of an adverse event or disease progression, patients are instructed to call and/or visit the clinic trials unit at Beth Israel Deaconess Medical Center. Any visits will be recorded on source documentation as Unscheduled Visits. Any of the procedures may be performed at an unscheduled visit at the discretion of the investigator.

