 - (i) clinical signs of inflammation, for example erythematous margins, sensations of itch, pain, dysaesthesia
 - (ii) lesions increasing in size or appearance of new lesions within the last 3 months
 - (iii) ulcerations
4. Subjects must be able to understand and communicate with the investigator and comply with the requirements of the study and must give a written, signed and dated informed consent before any study related activity is performed.

Exclusion Criteria

Eligible subjects will be excluded from participation if they meet any of the following criteria:

1. History of an ongoing, chronic or recurrent infectious disease, or evidence of tuberculosis infection as defined by a positive QuantiFERON TB-Gold test at screening.
2. Are currently pregnant, breastfeeding, or planning to get pregnant during the study.
3. Previous hypersensitivity reaction to secukinumab or to any of the components.
4. History of Inflammatory Bowel Disease (Crohn's Disease or Ulcerative Colitis)
5. Allergy to Latex
6. Currently on any other immunosuppressant systemic medication or within 28 days of baseline visit
7. Women of child-bearing potential, defined as all women physiologically capable of becoming pregnant, unwilling to use effective contraception during the study and for 16 weeks after stopping treatment. Methods of acceptable birth control are listed below under "Women of Childbearing Potential"
8. Subjects with a serum creatinine level exceeding 176.8 $\mu\text{mol/L}$ (2.0 mg/dL)
9. Screening total WBC count $<2,500/\mu\text{L}$, or platelets $<100,000/\mu\text{L}$ or neutrophils $<1,500/\mu\text{L}$ or hemoglobin <8.5 g/dL
10. Known infection with HIV, hepatitis B or hepatitis C at screening or randomization. Patients who are Hepatitis B Core antibody and/or Hep B Surface Antigen positive will be excluded from this study. Patients who are Hepatitis C ab positive will also be excluded from this study.
11. History of lymphoproliferative disease or any known malignancy or history of malignancy of any organ system within the past 5 years (except for non-melanoma skin cancer and carcinoma in situ of the cervix)
12. Are participating in another study using an investigational agent or procedure during participation in this study or within 28 days prior to baseline visit.
13. Plans for administration of live vaccines during the study period or 6 weeks prior to randomization

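### The two biopsy sites are not linked and slide reading is not masked to time point, so the histological change can reflect where the sample was taken

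*Combined protocol and SAP*

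**What the plan says.** The site rule is two sentences in B3.A, Skin Biopsy: "A 4 mm punch biopsy will be obtained from lesional skin at the baseline and week 26 visit", followed by "Skin biopsy location will be determined by the investigator", with standard biopsy technique. No section asks for the same lesion, the same zone or a set distance from the first punch, or for the site to be recorded. The Overview of Study Procedures schedules photographs from baseline to week 24 but does not connect them with the biopsies.

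On masking, B3.A states: "There will be no randomization or blinding. All subjects will receive study treatment". B3.B has the dermatopathologist assign the sub-scores, and is silent on whether time point is hidden.

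The pair of biopsies feeds three results:
- the secondary endpoint, the proportion improving on histological score, for which no threshold is given;
- the test in B3.B, Histological Score, where the "overall change in score will be calculated and compared using a paired T-test";
- the pre/post IL-17A comparison under Evaluation of immunohistochemistry.

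The antibody is specified as "Anti-Human IL17A antibody [Abcam 4K5F6] at a concentration of 0.5–10" µg/ml, with positive and negative controls run in parallel.

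**The concern.** All three results treat the within-subject difference as change under treatment. That is sound only if both punches sample comparable skin. The protocol itself describes lesions that are not uniform. Inclusion criterion 3(i) refers to "clinical signs of inflammation, for example erythematous margins", and B2 says of the plaques: "These plaques can become atrophic over time displaying a characteristic yellow hue". It is reasonable to expect active and quieter zones to score differently on infiltrate and histiocytes, although the documents give no figures.

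Pairing removes differences between subjects, not differences between sites within a subject. With no control group, nothing cancels a site effect. The person choosing the second site knows the treatment and can see which areas have improved, and a reader who knows the time point can add to the problem. Histology is the secondary endpoint closest to the IL-17 hypothesis, so an uninterpretable change there costs the pilot much of its mechanistic value.

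**Working it through.** The plan gives no alpha, power or effect size, so there is no figure of its own to reproduce. The check asks what the planned paired analysis would show with no drug effect.

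**From the documents:** n = 18; four items each scored 0–3, so a sum of 0–12; paired t-test.

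**Assumed:** per-biopsy SD σ = 1.0 to 1.5 points; gap between active and quieter zones g = 1 to 3 points; fraction f of subjects sampled in the active zone first and the quieter zone second; false improvement judged at one-sided 2.5%.

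**Formulas.** For a one-way shift, the change D (post minus pre) has mean −f·g and variance 2σ² + g²·f(1−f).

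**Worked case, f = 0.25, g = 2.** The mean change is −0.25 × 2 = −0.5.
- σ = 1.0: variance 2 + 4 × 0.1875 = 2.75, SD 1.66, SE 1.66/√18 = 0.39, ratio of mean to SE 0.5/0.39 = 1.28.
- σ = 1.5: variance 4.5 + 0.75 = 5.25, SD 2.29, SE 0.54, ratio 0.93.

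The critical value on 17 df is 2.11. Simulation with the change rounded to whole points (40,000 trials per setting) gives:

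| Site pattern, no drug effect | Mean change | False improvement (σ 1.0–1.5) |
|---|---|---|
| No shift | 0 | 2.4–2.6% |
| 25% active to quieter, gap 1 | −0.25 | 7–10% |
| 25% active to quieter, gap 2 | −0.5 | 13–21% |
| 25% active to quieter, gap 3 | −0.75 | 21–32% |
| 25% each way, gap 2 | 0 | about 2.5% |
| 25% down, 15% up, gap 2 | −0.2 | about 5–6% |
| 15% down, 25% up, gap 2 | +0.2 | about 1% |

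**Share of subjects with any fall.** This is nearer to the stated endpoint. It is 36–41% with no shift, about 49% with the one-way 25% shift and a 2-point gap, and 40–42% with 25% shifting each way.

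**Cross-check with a different model.** Assumptions: site SD within a subject 0.5–2 points, reader SD 0.5, subject mean 7 and SD 2; 20,000 trials.
- Matched sites: false improvement 2.3–2.6%; about 25% of subjects fall by at least 1 point.
- Both sites free and unselected: mean change 0, false improvement 2.5%; 31–43% fall by at least 1 point.
- Baseline from the more active of two sites, second site unselected: mean fall 0.28–1.08 points; false improvement 19–38%.

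The two models agree. The mean and the t-test are distorted only by a systematic shift; the proportion improving rises even without one.

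**The case against.** A reader might infer that the investigator picks a new site each time and that the endpoint is therefore biased towards benefit. The documents support neither step. The text permits a new site but does not require one, and returning to the same lesion is equally compatible with it. Lesional skin is required at both visits. In a partial responder, that could steer the second punch to residual disease and hide benefit. When shifts are balanced the t-test keeps its nominal rate, and a partly balanced pattern gives only about 5–6%.

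The zone gap, shifted share and SD are not in the documents, and collagen degeneration need not be higher at the margin. The endpoint is secondary, the analysis mainly descriptive, and the dermatopathologist, not the investigator, scores the slides. Much of the any-fall share arises from assumed noise and the missing threshold, not from site choice.

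A reader might also infer that stain concentration varies 20-fold (10/0.5) between slides. The range may simply be a working range from which one concentration is set, and controls run in parallel.

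All of this stands as a limit on direction and size. It does not supply the missing link between the two sites or the missing masking of slide reading.

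**Conclusion.** The point holds as a gap in the design, not as a demonstrated bias towards benefit. Because the plan neither links the two sites nor masks slide reading to time point, a histological change could not be attributed to treatment with confidence, whichever way it went.

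The size depends wholly on assumed inputs. A one-way shift in 25% of subjects gives false improvement in about 7–32% of trials; balanced shifts leave the nominal 2.5%. Even balanced shifts move the any-fall share from 36–41% to 40–42%. The primary IGA endpoint is unaffected. The antibody range is a secondary point. The change is worth making because it is cheap and closes both directions of bias.

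**What to change.** - **Site.** Amend both sentences of the Skin Biopsy section. Take the second biopsy from the same lesion and zone as the first, adjacent to but outside the baseline scar, with the site marked on the baseline study photograph. Make the lesional-skin requirement consistent with this for a zone that has cleared. If a different site is used on clinical grounds, the investigator records the reason.
- **Reading.** The existing dermatopathologist scores slides coded for time point. The protocol sets the IL-17A tiers from the pre-treatment biopsies, so set those tiers first, then recode all slides for scoring.
- **Staining (secondary).** State one fixed antibody concentration for all study slides, and stain each subject's pair in one run where tissue allows.
- **Subjects already biopsied.** The protocol mentions three completers and one early termination, for whom a baseline site rule comes too late. Apply coded reading to their retained slides and report their biopsy sites as far as recorded.
- **Timing.** The Skin Biopsy text puts the second biopsy at week 26. The schedule ticks it at week 24 and shows only suture removal at week 26. These must be reconciled in the same edit.

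The cost is protocol wording, slide coding, less freedom in choosing the second site, and later IL-17A scoring. No biopsy, visit or reader is added.
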